6. STUDY PROCEDURES

6.1 Schedule of Treatment Procedures and Evaluations

			Weeks									
	Phone/ Online Screen	Base- line	1 Start of Tx	2	3	4	5	6	7	8 End of Tx	12 (3 Month Follow- Up)	24 (6 Month Follow- Up)
Telephone/Online Screening	Х											
Compensation			\$30		\$30		\$30			\$40	\$60	\$70
Electronic Diary Assessments		Every	other day	surveys 1	from week	2 to wee	k 8; \$5 pe	r survey 1	or up to \$1	20 total		
TREATMENT PROCEDURES												
Virtual MBAT groups (MBAT & MBAT + iQuit Mindfully conditions)			Tx 1	Tx 2	Tx 3	Tx 4	Tx 5	Tx 6	Tx 7	Tx 8		
iQuit Mindfully text messages (iQuit Mindfully & MBAT + iQuit Mindfully conditions)		Text messages based upon participants' choice in frequency and timing of messages										
Self-Help Materials (all conditions)		Χ	X									
Nicotine Replacement Therapy Dispensation (all)			Participants receive 4 weeks of patches and lozenges in person at baseline, and then the remaining 4 weeks of patches are mailed.									
IN-PERSON ELIGIBILITY												
Carbon Monoxide		Х								Х	Х	Х
Cotinine (Saliva Sample)												Х
Screening for Depression and Substance Dependence		Х										
SMOKING												
Information for Setting Up Text Messages		Х										
Tobacco History	Х											
Smoking Status, use of other tobacco products, electronic vapor products, NRT, pharmacotherapy		Х	Х		Х		Х			Х	X	Х

	Phone/ Online Screen	Base- line	1 Start of Tx	2	3	4	5	6	7	8 End of Tx	12 (3 Month Follow- Up)	24 (6 Month Follow- Up)
Additional Resources Used for Smoking Cessation										Х	X	X
Wisconsin Inventory of Smoking Dependence Motives (WISDM)		Х								Х	Х	Х
Wisconsin Smoking Withdrawal Scale (WSWS)			Х		Х		Х			Х	Х	Х
Self-Efficacy Scale		Х	Х		Х		Χ			Х	Х	Х
MINDFULNESS												
Mindfulness Attention Awareness Scale (MAAS)		Х								Х	Х	Х
Five Facet Mindfulness Questionnaire (FFMQ short form)		Х								Х	Х	Х
Mindfulness Practice Frequency					Х		Х			Х	Х	Х
Self-Compassion Scale (short form)		Х								Х	Х	Х
STRESS/ NEGATIVE AFFECT												
Perceived Stress Scale		Х								Х	Х	Х
Positive and Negative Affect Scale		Х	Х		Х		Х			Х	Х	Х
Experiences with Discrimination		Х										
SOCIAL SUPPORT												
Multidimensional Scale of Perceived Social Support			Х							Х	Х	Х
Group Climate Questionnaire (MBAT & MBAT + iQuit Mindfully)										Х		
PROGRAM EVALUATION												
Text Message Feedback					Х		Х				Х	Х
Perceived Benefits										Х	Χ	Х
Program Evaluation Questionnaire										X		

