Aim II. Investigate the mechanisms through which mindfulness training impacts smoking cessation. Participants will complete questionnaires from baseline through 24 weeks after the start of treatment, in addition to intensive diary assessments for 6 contiguous weeks during treatment. We hypothesize that:

- 2a) Compared to UC, the mindfulness treatment arms (MBAT, iQuit Mindfully, and MBAT + iQuit Mindfully) will increase mindfulness; reduce negative affect (NA) and volatility of NA (i.e., greater affective stability); increase positive affect; reduce craving and withdrawal; and increase self-efficacy and social support, all of which will mediate effects of the mindfulness-based treatment arms vs. UC on abstinence.
- 2b) Compared to UC, MBAT, iQuit Mindfully, and MBAT + iQuit Mindfully will all attenuate links between NA/craving and smoking. That is, in addition to reducing NA and craving (2a), mindfulness training is hypothesized to weaken the relationships between NA/craving and smoking.

2c) Compared to MBAT, MBAT + iQuit Mindfully will produce stronger effects on the above mechanisms (2a, 2b). Mechanisms outlined in 2a will mediate effects of MBAT + iQuit Mindfully vs. MBAT on abstinence.

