For our previous smoking cessation study at GSU, the inclusion criteria were slightly more rigid. For example, interested individuals were excluded if they also used tobacco products other than cigarettes. Given that use of other tobacco products (e.g., cigars, little cigars, cigarillos) is common among low-income adult smokers, we believe it is important to include these people and help them quit smoking cigarettes as well as other tobacco products. Accordingly, we will contact individuals who expressed interest in our previous smoking cessation study and did not qualify at that time but might meet the current eligibility criteria. We will describe the current study and if they are interested, they will complete the same screening procedures as other potential participants.

Randomization. Randomization will take place at the end of the baseline session, after baseline assessments have been administered. Stratified permutated block randomization will be implemented. Block randomization can achieve balance in the number of assignments to each treatment group. This form of randomization can be conducted within each stratum (i.e., stratified permutated block design) in efforts to achieve both covariate balance and treatment balance. To Given the dangers of overstratification (e.g., with too many strata, there may be insufficient numbers of participants within each block), researchers have recommended using one or two stratification variables that are expected to be most strongly associated with the outcome. To Stratification will be conducted with respect to race/ethnicity and poverty status, both of which are predictors of smoking cessation success.

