- Tobacco History assesses onset of regular smoking, previous quit attempts, abstinence history, smoking rate, and partner smoking status. This includes the Heaviness of Smoking Index comprises two items from the Fagerström Test for Nicotine Dependence (FTND) ²⁹: self-reported average number of cigarettes smoked per day and time to first cigarette upon waking ("time to first cigarette"). The HSI is a strong indicator of nicotine dependence ³⁰.
- Smoking Status (SRNT) surveys tobacco use, use of other tobacco products, and nicotine replacement medications. Smoking Abstinence will be assessed according to the SRNT guidelines ³¹, which suggest reporting point prevalence abstinence (i.e., no smoking during

past week), continuous abstinence (i.e., no smoking since quit date), and time to relapse (i.e., any tobacco use over 7 consecutive days or 2 consecutive weeks). All self-reported abstinence will be biochemically confirmed by CO<6ppm. Use of novel tobacco products (e.g., e-cigarettes and heated tobacco products) will also be assessed. Participants will also indicate which forms of nicotine replacement therapy and/or pharmacotherapy (if any) they used in the past week.

- Additional resources used for smoking cessation will ask participants about various strategies
 for quitting smoking (e.g., acupuncture, hypnosis, other text messaging programs or mobile
 apps). This will allow the researchers to capture resources participants might be using to help
 them quit smoking apart from what they receive in the study.
- The *Brief Wisconsin Dependence Motives Questionnaire*³² is a 37-item measures that yields an overall dependence score and subscale scores for other dimensions (i.e., cognitive enhancement, affective enhancement, automaticity, affiliative attachment, loss of control, craving, cue exposure/associative processes, social/environmental goals, taste/sensory processes, weight control, tolerance).
- The Wisconsin Smoking Withdrawal Scale ³³ includes subscales for anger, anxiety, sadness, concentration difficulty, craving, hunger, and sleep. All subscales have excellent internal consistency and validity.³⁴
- The Self-Efficacy Scale assesses confidence for resisting smoking urges in specific types of situations (e.g., when feeling stressed, when with friends) ³⁵ Subscales include negative affect, pleasure, social image, social influence, and diet. Scores are predictive of relapse. ³⁶

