- Participants will complete *Program Evaluations* to provide for their feedback about and suggestions for improving the intervention (both MBAT and iQuit Mindfully text messages). Usual care participants will answer 1 program evaluation question: "On the scale below, please circle the number that best represents whether you would recommend this quit smoking program (or something similar) for others who are interested in quitting smoking." (rated on 1-10 scale).

The maximum time between telephone screening and enrollment will be 1 month. The maximum time between baseline assessment and start of treatment will be 1 month. However, we will employ a variety of strategies to ensure that these timeframes are as short as possible. For example, in order to reduce the time between telephone screening and baseline we will offer a variety of days and times for baseline assessment. We will also time our recruitment efforts around planned baseline assessments to maximize potential participants' interest (in order to prevent longer wait time to accrue a sufficient number of participants to start a group).

Electronic Diary Assessments. *Electronic Diary Assessments* (also referred to as short-surveys) will be administered in the evening on every other day from Week 2 to Week 8, thus capturing key processes surrounding quitting smoking. Diary assessments will assess smoking behavior ("How many cigarettes did you smoke today?") and each of the hypothesized mechanisms (mindfulness, emotions, craving and withdrawal, self-efficacy, and social support). Participants will also indicate their mindfulness practice that day (See Appendix). Participants will receive an email and/or text with the REDCap link to the electronic diary assessment survey. Both participant-initiated options allow respondents to complete assessments at a time that is convenient to them between that evening and the next morning (by 9am).

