 pilot study virtual sessions, some participants did not have a private place to join. Being able to
 use a tablet in a private room at GSU would provide a solution.
- MBAT participants will attend a group Zoom orientation within two weeks before the first treatment session. This will give them a chance to meet each other, practice using Zoom together (e.g., muting/unmuting, turning camera on and off), and ask questions of the study staff.

- When participants connect to Zoom, study staff will admit them individually into a separate breakout room to ensure that they are in a private location and troubleshoot any issues.
- We will encourage participants to join Zoom sessions a few minutes early so that they have a chance to get to know their fellow group members better.
- Both mindfulness instructors (certified Mindfulness-Based Stress Reduction teachers through the University of Massachusetts Medical School) have experience leading online mindfulness groups through Zoom and will draw on their past experience. For example, they will encourage participants to stay unmuted during discussion to facilitate natural conversation (unless there is excessive background noise); mute participants during mindfulness practices; and provide brief breaks.

*GSU continues to update guidelines for on-campus research. We will follow updated guidelines as they become available.

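### The withdrawal/craving scale (WSWS) and the social support scale (MSPSS), which measure hypothesis 2a mediators, are first given after randomisation, so Aim II has no pre-randomisation value for either

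*Combined protocol and SAP*

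**What the plan says.** Section 1, hypothesis 2a, predicts that the mindfulness arms, compared with usual care (UC), will "reduce craving and withdrawal; and increase self-efficacy and social support, all of which will mediate effects" on abstinence. Sections 1 and 9 both say that the questionnaire data for Aim II run from baseline to week 24.

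Section 6.1 marks the "Multidimensional Scale of Perceived Social Support" at weeks 1, 8, 12 and 24, and the WSWS at weeks 1, 3, 5, 8, 12 and 24. Neither row has a Baseline mark. Section 6.2 says that the WSWS "includes subscales for anger, anxiety, sadness, concentration difficulty, craving, hunger, and sleep", so it carries both withdrawal and craving.

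On timing, Section 4 states: "Randomization will take place at the end of the baseline session, after baseline assessments have been administered". Section 6.2 adds: "The maximum time between baseline assessment and start of treatment will be 1 month". Week 1 is labelled as the start of treatment.

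**The concern.** Hypothesis 2a is worded as increases and reductions, and its other questionnaire mediators (mindfulness, affect, self-efficacy) all have a baseline score. Withdrawal and social support do not, and the plan gives no reason for the difference and no rule for handling it.

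Four things are at stake:

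- Change from a pre-randomisation value cannot be computed for these scales.
- The treatment-to-mediator comparison loses precision, most of all in contrasts with the 50-person UC arm.
- The missing-data paragraph of Section 9 imputes from baseline responses and other covariates. For these scales there is no baseline response, and anyone lost before week 1 contributes no value at all.
- Mediator levels are not randomised. Without the prior level, the mediator-to-abstinence path cannot be adjusted for differences in support or withdrawal that were present before randomisation.

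**Working it through.** The plan gives no figure to reproduce here, so the check is of the schedule first and of size second.

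**1. Schedule rows, read against the column headers of Section 6.1**

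| Scale | Baseline | Week 1 | Other marks (weeks) |
|---|---|---|---|
| WSWS (withdrawal, craving) | none | yes | 3, 5, 8, 12, 24 |
| MSPSS (social support) | none | yes | 8, 12, 24 |
| Self-efficacy | yes | yes | 3, 5, 8, 12, 24 |
| Positive and negative affect | yes | yes | 3, 5, 8, 12, 24 |
| Mindfulness (MAAS) | yes | none | 8, 12, 24 |
| Dependence motives (WISDM) | yes | none | 8, 12, 24 |

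The self-efficacy and affect rows carry both a Baseline and a week 1 mark. The empty Baseline cells for WSWS and MSPSS are therefore not a column shift from text extraction.

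**2. What happens between randomisation and week 1**

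- Randomisation is the last step of the baseline visit (Section 4), and treatment starts up to one month later (Section 6.2).
- All arms are handed nicotine replacement at baseline (Section 5).
- "MBAT participants will attend a group Zoom orientation within two weeks before the first treatment session" (Section 6.2).
- The week 1 survey is done remotely. Its order relative to the first session or the first text messages is not stated.
- The electronic diaries start in week 2 (Section 6.2), so they supply no earlier value.

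The first measurement on either scale is thus post-randomisation on any reading of the timeline.

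**3. Illustrative size for one mindfulness arm against UC**

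Inputs from Section 9 (Power and Sample Size): 145 per active arm, 50 in UC, 20% attrition, two-sided 0.05.

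Assumptions: d=0.35, which the plan quotes for abstinence and not for any mediator; a single follow-up time point; and a baseline-to-follow-up correlation r, which the documents do not give.

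- Completers: 145 × 0.8 = 116 and 50 × 0.8 = 40.
- Standard error in SD units: √(1/116 + 1/40) = 0.1834.
- Adjusting for baseline multiplies the variance by 1 − r², so power = Φ(0.35 / [√(1 − r²) × 0.1834] − 1.96).

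| r | 1 − r² | Power |
|---|---|---|
| 0 (no baseline) | 1.00 | Φ(−0.05) = 48% |
| 0.3 | 0.91 | Φ(0.04) = 52% |
| 0.5 | 0.75 | Φ(0.24) = 60% |
| 0.7 | 0.51 | Φ(0.71) = 76% |

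With no attrition (145 against 50), the same formula gives 57%, 61%, 69% and 85%.

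**The case against.** The strongest reply is that randomisation already protects the comparison. Hypothesis 2a is framed against UC, and follow-up scores can be compared between arms without bias and without a baseline. This stands. A reader might infer from the missing baseline that the treatment-to-mediator tests for these scales are invalid, and the documents do not support that.

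Four further points limit the concern.

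- **Craving is not wholly unmeasured at baseline.** The WISDM is given then and has a craving subscale, so a claim that craving has no baseline at all would go too far. It is a dependence-motives measure with no assessment at weeks 1, 3 or 5, so it is a partial proxy for the WSWS craving score and not its baseline.
- **The orientation need not move social support.** It is tempting to say that meeting the group contaminates the week 1 score in the MBAT arms. But MSPSS asks about support from relatives, friends and a partner, and group cohesion has its own questionnaire. Nothing in the documents shows that the orientation would shift MSPSS.
- **Week 1 may precede quitting.** MBAT participants choose a quit date from day 7 to day 30, and nicotine replacement is dispensed to every arm alike. Week 1 could be a sensible pre-quit reference for withdrawal. It is still post-randomisation, and the argument does nothing for social support.
- **The plan never proposes week 1 as a covariate.** Adjusting for it could remove part of an early effect, but that is a step to rule out, not one the plan takes.

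The power figures are also open to challenge. The effect size is borrowed from abstinence, r may be low for withdrawal measured while still smoking, and the data are repeated measures. Section 9 already adjusts for demographics and baseline dependence, so the added gain may be smaller than shown.

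**Conclusion.** The gap is real and modest. WSWS and MSPSS have no pre-randomisation measurement, although Sections 1 and 9 say that Aim II questionnaire data start at baseline, and the plan does not say how these mediators are handled. Withdrawal and social support have no baseline measure at all, and craving has only a proxy. The loss is in change scores, precision, imputation and adjustment of the mediator-to-abstinence path, and not in the validity of between-arm follow-up comparisons. The primary abstinence outcomes are untouched.

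The schedule finding rests on the documents alone. The size does not: the gain from 48% to between 52% and 76% depends on the assumed d, r and single time point, and should be read as illustration only. The case for acting is that the remedy is cheap.

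**What to change.** 1. **Schedule (Section 6.1).** Give MSPSS and WSWS at the baseline visit, before randomisation. MSPSS (12 items) can be moved from week 1, which adds no burden and gives it the same pattern as the mindfulness scales; the price is that it then has no week 1 score. WSWS is added at baseline, and its week 1 form stays as a post-randomisation value.
2. **Analysis (Section 9).** The covariate list names no baseline mediator values. Add the baseline MSPSS and WSWS scores as covariates in the Aim II mediator and outcome models, and make them available to the imputation model.
3. **Participants already enrolled.** Analyse these two mediators without a baseline, and state that week 1 is not used as one. Say in advance how participants with and without a baseline score will be combined.
4. **Wording.** If the schedule cannot be changed, correct Sections 1 and 9 to say that these scales start at week 1, after randomisation.

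The cost is an amendment to the schedule and a few extra minutes in the baseline questionnaire battery.

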6.2 Description of Evaluations

Screening Evaluation and Consenting Procedure

Telephone Screening. Interested individuals who prefer to complete initial screening by telephone will be given a detailed description of the study over the phone. The voluntary nature of the study will be emphasized, and it will be made clear that if they decide not to participate, there will be no repercussions. Research staff will read the telephone consent form to potential participants and answer any questions. After provision of verbal informed consent (a Waiver of Documentation of Consent has been included in the GSU IRB protocol), the research staff member will document verbal consent and sign and date the consent form through REDCap. Potential participants will then be screened for inclusion/exclusion and answer questions about demographic information (to be documented through Qualtrics as noted below). Eligible individuals who are interested in participating will be scheduled for an initial in-person session. Participants will receive a reminder telephone call, text, and/or email on the day before their scheduled session.

Online Screening. Individuals who click on the study link through an advertisement or digital flyer will be taken to an online (GSU-hosted Qualtrics) screener survey. Before beginning the survey, participants will be given information about the study, including the voluntary nature of the study, through an online informed consent form. After providing consent, participants can complete the survey online. Data collected via this screener survey will be encrypted with access limited to select study personnel. Eligible individuals who are interested in participating will provide their contact information in order for research staff to contact them by phone to confirm eligibility and answer any

questions. Eligible individuals who are interested in participating will then be scheduled for an initial inperson session. Participants will receive a reminder telephone call, text, and/or email on the day before their scheduled session. Qualtrics includes survey protection features to prevent people from taking an online survey more than once. If it appears that an individual has attempted more than one screening method (e.g., telephone and online), research staff will call the person again to confirm eligibility and resolve any inconsistencies if needed.

In-Person Baseline Visit and Consent Procedure. Following the telephone or online screener, interested individuals will attend an in-person session to finalize eligibility, engage in further discussion about the study, and provide written informed consent.

Before in-person assessment of eligibility criteria, participants will review the consent form for in-person screening. Study personnel will offer an opportunity for participants to ask questions and have them answered, the consent form for in-person screening will be signed and dated by the participant and staff member, and a copy of this form will be given to the participants. Then, in order to confirm eligibility, participants will provide a breath sample for assessment of expired carbon monoxide. Health literacy will be assessed with the Rapid Estimate of Adult Literacy in Medicine (REALM²¹), and for the proposed study participants who have at least a sixth-grade level will be eligible. Individuals who decline or are ineligible will be given self-help materials and referral to other cessation programs. In addition, potential participants will complete the Patient Health Questionnaire-2 PHQ-2; ^{22,23} and Severity of Dependence Scale (SDS²⁴) in order to screen for clinically significant depressive symptoms and substance dependence, respectively. Individuals who are not eligible for these reasons will be provided with appropriate mental health referrals in addition to smoking cessation referrals.

Next, the research staff will engage eligible individuals in a discussion of pros and cons of participating, as well as participants' ambivalence about behavior change and research participation (these methods have been suggested to improve retention²⁵).

For eligible individuals who are interested in participating, study personnel will initiate the informed consent process which will include: 1) A thorough review of the Informed Consent Form (ICF; see Appendix), particularly study procedures; 2) Study personnel will offer an opportunity for participants to ask questions and have them answered; 3) The ICF will be signed and dated by the participant and staff member; and 4) A copy of the ICF will be given to the participants.

Participants will be given the choice of using their own tablet or laptop computer or one provided by the study. For participants in MBAT and MBAT + iQuit Mindfully conditions, study personnel will explain the requirements for joining the treatment session via the video conferencing program, Zoom. Research staff will conduct separate sessions with participants to ensure they can access Zoom.

Participants who choose to use the basic tablet provided by the study will include those who:

- -do not own a tablet or other device with a web camera,
- -do not have access to consistent wireless internet needed to join virtual group sessions, or -prefer to use a study tablet

Participants will be given the choice of using their own mobile phone or one provided by the study. For participants in the iQuit Mindfully and MBAT + iQuit Mindfully conditions, study personnel will explain the text messaging procedures in detail and send a test message to the participant, who will respond and ask any questions.

Participants who choose to use the basic cellphone provided by the study will include those who:
-do not own a wireless cellphone,

- -do not own a wireless cellphone that can receive and send phone calls, SMS and MMS messages,
- -prefer to use a study phone, or
- -do not have consistent phone service with a working number

These participants will have the option of borrowing a study device for the duration of the study. The research team will explain to participants that all wireless devices must be returned. Mobile phones must be returned by the final week 24 assessment, and tablets must be returned at the week 8 assessment. Wireless devices that are borrowed will be wiped upon returning them to the research team. All sim-cards will be wiped clean. New sim-cards will be used for each participant requesting a phone. All data collected via text message will be stored either on the Mobile Commons platform or the REDCap platform. No data will be saved to the device. For text messages and all other data remaining on the study devices when they are turned in from participants, the research team will wipe and reset the device.

Individuals who would like to participate and express informed consent will then be asked to complete questionnaires (see Appendix). Questionnaires will be administered through REDCap, to be taken either in-person at GSU (baseline and weeks 8, 12, and 24) or off site (REDCap links to be emailed/texted when participants do not come to GSU in person). See Table 6.1 for schedule of questionnaire assessments. Descriptions of the assessments are provided below:

- The *Telephone Screening* assesses eligibility criteria and demographic characteristics, including age, race, ethnicity, education, employment, and income.
- The *Patient Health Questionnaire-2* PHQ-2; ^{22,23} is a 2-item questionnaire designed to screen for symptoms of depression. Participants are asked, "Over the last 2 weeks, how often have you been bothered by the following problems?": "feeling down, depressed or hopeless" and "little interest or pleasure in doing things." These items which correspond to the two core diagnostic criteria for Major Depressive Disorder; ²⁶ are rated on a 0-3 scale (0 = not at all, 3 = nearly every day). Individuals with scores of 3 or above which has been identified as the cut-off for obtaining optimal sensitivity and specificity for identifying depressive disorders; ^{22,23} will not be eligible but will be provided with appropriate mental health referrals.
- The Severity of Dependence Scale (SDS) is a 5-item questionnaire that measures the extent of psychological dependence on illicit drugs in the past 12 months.²⁴ The scale has been validated for several illicit drugs including cannabis, cocaine, amphetamines, benzodiazepines, and heroin. Each of the five items is scored on a 4-point scale ranging from 0 (Never/Almost Never) to 3 (Always/Nearly Always) and summed for a total score. Individuals with scores of 4 or higher^{27,28} will not be eligible but will be provided with appropriate mental health referrals.
- The Information for Setting Up Text Messages questions assess participants' amount of money spent on cigarettes, personal reasons for quitting, preferences about timing and frequency of text messages, and quit date. This information is incorporated into iQuit Mindfully to personalize the content, frequency and timing of text messages.
- Tobacco History assesses onset of regular smoking, previous quit attempts, abstinence history, smoking rate, and partner smoking status. This includes the Heaviness of Smoking Index comprises two items from the Fagerström Test for Nicotine Dependence (FTND) ²⁹: self-reported average number of cigarettes smoked per day and time to first cigarette upon waking ("time to first cigarette"). The HSI is a strong indicator of nicotine dependence ³⁰.
- Smoking Status (SRNT) surveys tobacco use, use of other tobacco products, and nicotine replacement medications. Smoking Abstinence will be assessed according to the SRNT guidelines ³¹, which suggest reporting point prevalence abstinence (i.e., no smoking during

past week), continuous abstinence (i.e., no smoking since quit date), and time to relapse (i.e., any tobacco use over 7 consecutive days or 2 consecutive weeks). All self-reported abstinence will be biochemically confirmed by CO<6ppm. Use of novel tobacco products (e.g., e-cigarettes and heated tobacco products) will also be assessed. Participants will also indicate which forms of nicotine replacement therapy and/or pharmacotherapy (if any) they used in the past week.

- Additional resources used for smoking cessation will ask participants about various strategies
 for quitting smoking (e.g., acupuncture, hypnosis, other text messaging programs or mobile
 apps). This will allow the researchers to capture resources participants might be using to help
 them quit smoking apart from what they receive in the study.
- The *Brief Wisconsin Dependence Motives Questionnaire*³² is a 37-item measures that yields an overall dependence score and subscale scores for other dimensions (i.e., cognitive enhancement, affective enhancement, automaticity, affiliative attachment, loss of control, craving, cue exposure/associative processes, social/environmental goals, taste/sensory processes, weight control, tolerance).
- The Wisconsin Smoking Withdrawal Scale ³³ includes subscales for anger, anxiety, sadness, concentration difficulty, craving, hunger, and sleep. All subscales have excellent internal consistency and validity.³⁴
- The Self-Efficacy Scale assesses confidence for resisting smoking urges in specific types of situations (e.g., when feeling stressed, when with friends) ³⁵ Subscales include negative affect, pleasure, social image, social influence, and diet. Scores are predictive of relapse. ³⁶
- The Mindful Attention Awareness Scale MAAS; ³⁷ is a 15-item self-report measure of dispositional mindfulness that has shown good reliability and validity.³⁷
- The Five-Facet Mindfulness Questionnaire-Short Form³⁸ is a 24-item self-report questionnaire of facets of dispositional mindfulness. The scale yields five factors: 1) Nonreactivity, 2) Observing, 3) Acting with Awareness, 4) Describing/Labeling with Words, and 5) Nonjudging of Experience, with strong psychometric properties.
- The Self-Compassion Scale Short Form⁴⁵ is a 12-item self-report measure of self-compassion. Subscales include self-kindness, self-judgement, common humanity, isolation, mindfulness, and over-identification.⁴⁵
- Participants will fill out a *Mindfulness Practice Log*¹² to indicate how frequently they practice each of the mindfulness techniques taught in treatment.
- The *Perceived Stress Scale*³⁹ is a 10-item self-report measure of the extent to which individuals view their lives as stressful. The scale shows good psychometric properties.
- The Positive and Negative Affect Schedule (PANAS ⁴⁰) is a 20-item self-report measure of affective experience yielding two factors (Positive and Negative Affect) with strong psychometric properties ⁴⁰.
- The *Multidimensional Scale of Perceived Social Support*⁴¹ is a 12-item scale, with subscales assessing perceived social support from family, friends, and significant others.
- The *Group Climate Questionnaire* (*GCQ-S*)⁴⁸ is a 12-item self-report scale which measures climate and cohesion of the group (only applicable for MBAT participants). Sub-scales include engaged, conflict, and avoiding.⁴⁸
- Participants will be asked to provide feedback about their experiences receiving the text messages (Text Message Feedback).

- Participants will complete 4 items to indicate perceived benefits of the quit smoking program. As described by Hoeppner et al. (2017),⁴² participants rate the extent to which the program gave them confidence to quit smoking, made them think that it was worthwhile to quit, made them feel that someone cared if they quit, and made them feel that they knew the right steps to take to quit. Items are rated from 1 (completely disagree) to 5 (completely agree).
- Participants will complete *Program Evaluations* to provide for their feedback about and suggestions for improving the intervention (both MBAT and iQuit Mindfully text messages). Usual care participants will answer 1 program evaluation question: "On the scale below, please circle the number that best represents whether you would recommend this quit smoking program (or something similar) for others who are interested in quitting smoking." (rated on 1-10 scale).

The maximum time between telephone screening and enrollment will be 1 month. The maximum time between baseline assessment and start of treatment will be 1 month. However, we will employ a variety of strategies to ensure that these timeframes are as short as possible. For example, in order to reduce the time between telephone screening and baseline we will offer a variety of days and times for baseline assessment. We will also time our recruitment efforts around planned baseline assessments to maximize potential participants' interest (in order to prevent longer wait time to accrue a sufficient number of participants to start a group).

Electronic Diary Assessments. *Electronic Diary Assessments* (also referred to as short-surveys) will be administered in the evening on every other day from Week 2 to Week 8, thus capturing key processes surrounding quitting smoking. Diary assessments will assess smoking behavior ("How many cigarettes did you smoke today?") and each of the hypothesized mechanisms (mindfulness, emotions, craving and withdrawal, self-efficacy, and social support). Participants will also indicate their mindfulness practice that day (See Appendix). Participants will receive an email and/or text with the REDCap link to the electronic diary assessment survey. Both participant-initiated options allow respondents to complete assessments at a time that is convenient to them between that evening and the next morning (by 9am).

Saliva Samples for Cotinine Analysis. At the last study visit (approximately 24 weeks after the start of treatment), participants will provide a saliva sample by placing an oral swab under their tongue for 1-2 minutes (Salimetrics; https://www.salimetrics.com/collection-method/oral-swab-saliva-collection-device/). Per Salimetrics instructions, consumption of alcohol, caffeine, nicotine and prescription/over-the-counter medications within the past 12 hours, as well as presence of oral diseases or injury, will be documented. Participants will rinse their mouth with water to remove any food residue and wait at least 10 minutes after rinsing before collecting saliva. The saliva sample will then be stored in a locked freezer situated in a locked room in the GSU Urban Life Building, only coded with an ID number and no personally identifying information. Swabs will be mailed to the Salimetrics lab for cotinine analysis, and the Salimetrics lab will discard the saliva after 1 year. Self-reported 7-day abstinence will be confirmed by saliva cotinine <20 ng/ml. 12,43 Use of NRT and other nicotine-containing products (e.g., e-cigarettes) will be assessed to ensure that saliva cotinine levels are not affected by non-combusted nicotine products. Participants who do not attend the in-person 24-week assessment visit will be asked to provide a saliva cotinine sample via mail.

*Procedures for Participant and Research Team Safety in the Context of the COVID-19 Pandemic

The current study design involves in-person sessions at GSU. During the COVID-19 pandemic, inperson procedures will follow the Georgia State Standard Public Health Precautions for On-Campus Visits Related to Human Subjects Research. For example:

- Pre-visit phone screening and arrival phone screening will be conducted to inquire about possible COVID-19 symptoms and exposure.
- Visitors cleared for study visits will be advised that they must wear face mask coverage while on campus. Research staff will also wear masks.
- Signage to encourage hand hygiene, respiratory hygiene, cough etiquette, and social distancing will be posted in and around the Waiting Area and Research Space.
- All visitors will be directed to wash hands or use hand sanitizer upon entry to Waiting Area/Research Space. Hand sanitizer will be provided.
- Researchers will wash hands or use hand sanitizer prior to and after each participant visit.
